### 3 - Results

A total of 500 breast cancer patients were included in the final analysis. Descriptive statistics revealed a high prevalence of psychological distress within the sample, with elevated scores in depression, anxiety, and stress domains.

Spearman correlation analysis revealed strong positive associations between sleep difficulty and psychological outcomes: depression ( $r = 0.85$ ), anxiety ( $r = 0.77$ ), and stress ( $r = 0.85$ ), all statistically significant at  $p < 0.001$ . Use of sedatives was also significantly correlated with elevated distress scores ( $r > 0.90$  across models).

Kruskal-Wallis tests demonstrated statistically significant differences in mean ranks of depression, anxiety, and stress across cancer stages ( $p < 0.01$ ), with higher distress in patients with advanced-stage disease.

Multivariate linear regression identified the following as significant predictors of psychological distress:

- PHQ9\_Total:  $\beta = 0.42$ ,  $p < 0.001$
- Anger:  $\beta = 2.08$ ,  $p < 0.001$
- Cancer Stage:  $\beta = 0.92$ ,  $p = 0.0014$

Psychological support was not a significant predictor ( $p = 0.606$ ).

Binary logistic regression showed that PHQ9 and anger significantly predicted severe anxiety, with odds ratios of 1.32 and 1.27, respectively ( $p < 0.001$ ). Stage of disease also emerged as a significant factor in anxiety prediction.

Receiver Operating Characteristic (ROC) curve analysis yielded an Area Under the Curve (AUC) of 0.74 for stress in predicting severe anxiety, indicating a fair level of discriminative ability.

Finally, conceptual path analysis demonstrated that the relationship between stress and anxiety was primarily indirect, mediated through sleep disturbance and daily performance impairment. The direct path from stress to anxiety was negligible ( $r = -0.01$ ), suggesting a mediated mechanism of action.

**Table 1.** Descriptive Statistics of Study Variables

Variable	N	Minimum	Maximum	Mean	SD
Total Cost	500	80	34785	3721.69	4456.79
PHQ9_Total	500	1	27	17.99	6.11
GAD7_Total	500	1	21	12.79	3.81
Cancer Stage	500	0	4	2.52	1.09
Children	500	0	5	2.53	1.63
Metastatic	500	0	1	0.36	0.48
Stress Level	500	0	4	2.64	0.79

The descriptive characteristics of the study variables are presented in **Table 1**. Depression and anxiety scores were moderately high, while stress levels were also elevated. Treatment cost showed substantial variability across participants.

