**Table 5:** Binary Logistic Regression – Predicting Severe Anxiety

Predictor	Odds Ratio (OR)	95% CI	P-value
Depression (PHQ-9)	1.32	1.18 – 1.56	<0.001

Anger	1.27	1.11 – 1.49	0.002
Stress Level	1.14	1.03 – 1.35	0.017
Psychological Support	0.54	0.33 – 0.91	0.021
Cancer Stage	0.61	0.33 – 0.87	0.049

[figure not shown]
Binary logistic regression (**Table 5**) showed that depression, anger, and stress significantly increased the odds of severe anxiety, while psychological support and advanced cancer stage were protective. The corrected model (**Table 6**) confirmed these associations.

**Table 6.** Logistic Regression Predicting Severe Anxiety (Corrected Model)

Predictor	Coef. ( $\beta$ )	Std. Error	z-value	p-value	95% CI (Lower – Upper)
PHQ9_Total	0.42	0.06	6.92	<0.001	0.30 – 0.53
Anger	2.08	0.48	4.36	<0.001	1.14 – 3.02
Psych Support	-0.18	0.34	-0.52	0.606	-0.84 – 0.49
Cancer Stage	0.92	0.29	3.20	0.0014	0.36 – 1.48

[figure not shown]
This table presents the corrected logistic regression model for predicting severe anxiety. PHQ9\_Total and anger were significant positive predictors, while psychological support did not show a significant protective effect in the adjusted model.

**Figure 2.** ROC Curve for stress predicting severe anxiety.

The ROC curve (**Figure 2**) illustrates the predictive value of stress scores for severe anxiety, with an AUC of 0.74 ( $p < 0.001$ ), indicating fair discriminative accuracy.

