#### 4- Discussion

The present study provides a comprehensive psychosocial profile of breast cancer patients in Al-Anbar, Iraq, highlighting significant associations between psychological distress, sleep disturbance, disease stage, economic burden, and emotional regulation. The results of our study reveal that depression and anxiety levels were remarkably high among breast cancer patients, with strong correlations to sleep-related variables and the use of sedative medications. These findings are consistent with previous studies from Iraq and neighboring countries, which emphasize the underrecognized psychological morbidity among cancer patients (13).

Specifically, the elevated stress levels observed in our study appear closely tied to poor sleep quality and increased reliance on sedatives. This pattern is consistent with findings from Iranian oncology research, where 66.8% of cancer patients reported poor sleep quality (PSQI > 5), strongly associated with symptoms of anxiety and depression (14)

Similarly, (14) Demonstrated that more than one-third of cancer patients experienced subjective sleep disturbances, with 6.1% relying on sedative medication. These findings highlight disrupted sleep as a key contributor to psychological distress in oncological care and support the growing understanding that impaired sleep quality may serve as a potential clinical indicator of emotional dysregulation in cancer care.

However, other studies have reported conflicting results. For example, (15) found that while sleep disturbances were prevalent among cancer patients, they were not consistently associated with heightened anxiety or depression. Such discrepancies may be explained by differences in patient populations, cancer types, cultural factors, and methodological variations across studies.

The results of the current study revealed that advanced cancer stage was significantly associated with increased levels of psychological distress, particularly anxiety and depression. After adjusting for stage coding, regression models confirmed that advanced cancer stage predicted elevated anxiety scores ( $\beta = 0.92$ ,  $p = 0.001$ ), which aligns with previous findings from oncology populations in the region(16). This association may reflect the psychological impact of disease severity, poor prognosis, increased treatment burden, and concerns about disease progression and its potential complications.

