Furthermore, Kruskal-Wallis analysis confirmed significant differences in mean ranks of depression, anxiety, and stress across cancer stages ( $H = 14.76$  to  $31.09$ ,  $p < 0.01$ ). These findings are supported by evidence from Iran and neighboring countries, where patients with stage III and IV breast cancer reported higher rates of emotional distress compared to the early stages of the disease (14). The increased psychological vulnerability in advanced stages underscores the need for stage-specific psychosocial interventions in cancer care protocols

Interestingly, total treatment cost showed a weak but statistically significant inverse correlation with psychological distress variables (e.g., PHQ-9\_Total:  $r = -0.11$ ,  $p = 0.017$ ). Although initially counterintuitive, this finding may reflect a perceived sense of security or access to higher-quality care among patients with greater financial capacity. Similar interpretations were reported in recent findings from Turkey, where patients with access to private sector services and higher financial resources exhibited lower levels of psychological distress despite elevated treatment costs, suggesting that financial ability may buffer emotional burden through enhanced control and perceived care quality (17).

As for psychological support, logistic regression models from this study suggested a protective effect ( $OR = 0.54$ ), though this was not statistically significant in the adjusted model ( $p = 0.606$ ). The lack of significance may be attributed to limited availability or underutilization of structured psychological services in the region, a challenge frequently reported in Iraq and across low-resource Middle Eastern settings. (18,19). Nonetheless, the direction of effect emphasizes the urgent need to integrate psychosocial support into routine oncology care.

Among all predictors examined, depression (PHQ9\_Total) and anger emerged as the strongest independent predictors of severe anxiety in both logistic and linear regression models ( $\beta = 0.42$  and  $2.08$ , respectively,  $p < 0.001$ ). These findings support prior research indicating that depressive symptomatology often precedes or co-occurs with anxiety in cancer patients, especially when emotional regulation is compromised (11)

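### The corrected logistic model for severe anxiety (Table 6) is said to confirm Table 5, but stage reverses, support loses significance, stress disappears, and the text reports its coefficients as linear regression

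*Combined protocol and SAP*

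**What the plan says.** Section 2-6 Data Analysis plans binary logistic regression for severe anxiety, and separate linear models for PHQ-9, GAD-7 and stress.

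Section 3 - Results then gives two logistic tables:

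- **Table 5** has five predictors, reported as odds ratios. The text under it says that depression, anger and stress raise the odds, that "psychological support and advanced cancer stage were protective", and that the corrected model "confirmed these associations".
- **Table 6**, captioned as the corrected model, has four predictors, reported as log-odds coefficients. The text under it says that "psychological support did not show a significant protective effect in the adjusted model". It does not comment on stage.

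The opening text of the Results states "Multivariate linear regression identified the following as significant predictors of psychological distress" and lists 0.42, 2.08 and 0.92, adding "Psychological support was not a significant predictor" with p = 0.606. It goes on: "Binary logistic regression showed that PHQ9 and anger significantly predicted severe anxiety, with odds ratios of 1.32 and 1.27, respectively".

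The Discussion says "After adjusting for stage coding, regression models confirmed that advanced cancer stage predicted elevated anxiety scores", citing 0.92. On support it says "logistic regression models from this study suggested a protective effect" (OR 0.54), not significant in the adjusted model (p = 0.606). It attributes 0.42 and 2.08 to logistic and linear models alike. The Conclusion names advanced stage as a main predictor of greater anxiety and depression.

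**The concern.** The report has one logistic outcome and offers two sets of estimates for it, telling the reader that they agree. On stage they point in opposite directions, and the sentence under Table 5 says the reverse of the Conclusion. A reader cannot tell which fit is the study's result, because the opening Results text takes its odds ratios from one table and its coefficients from the other.

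The model label matters as well. A coefficient of 0.92 from a logistic model is a change in the log-odds of severe anxiety. Called a linear regression result, or an effect on anxiety scores, it looks like about one point on a scale.

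For support, the Discussion sets the Table 5 odds ratio beside the Table 6 p-value, then uses the direction of the estimate to urge that psychosocial support be built into routine care.

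**Working it through.** **Step 1. Is Table 6 consistent with itself?** With z = coefficient/SE:

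- PHQ-9: 0.42/0.06 = 7.00 (printed 6.92)
- Anger: 2.08/0.48 = 4.33 (4.36)
- Support: -0.18/0.34 = -0.53 (-0.52)
- Stage: 0.92/0.29 = 3.17 (3.20)

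The stage interval, 0.92 ± 1.96 × 0.29, is 0.352 to 1.488 (printed 0.36 to 1.48), and z = 3.20 gives p = 0.0014 as printed. Table 6 reproduces within rounding.

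**Step 2. Put Table 6 on the scale of Table 5.** OR = exp(coefficient), with the printed limits exponentiated in the same way.

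| Predictor | Table 5 OR (95% CI), p | Table 6 OR (95% CI), p | Direction and significance both kept? |
|---|---|---|---|
| PHQ-9 | 1.32 (1.18 to 1.56), <0.001 | 1.52 (1.35 to 1.70), <0.001 | Yes |
| Anger | 1.27 (1.11 to 1.49), 0.002 | 8.00 (3.13 to 20.5), <0.001 | Yes, but size very different |
| Stress | 1.14 (1.03 to 1.35), 0.017 | no row | No |
| Support | 0.54 (0.33 to 0.91), 0.021 | 0.84 (0.43 to 1.63), 0.606 | No: significance lost, direction kept |
| Stage | 0.61 (0.33 to 0.87), 0.049 | 2.51 (1.43 to 4.39), 0.0014 | No: direction reversed, significant in both |

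Two of the five associations survive. For anger, the ratio of log coefficients is 2.08/ln(1.27) = 2.08/0.239 = 8.7.

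**Step 3. Would a stage recoding explain it?** Assume that Table 5 used a reversed linear stage code. Its odds ratio becomes 1/0.61 = 1.64, with limits 1/0.87 = 1.15 and 1/0.33 = 3.03. That agrees in direction with 2.51, leaving a gap of 2.51/1.64 = 1.5-fold. Reversing a linear code changes only the sign of that coefficient (and the intercept). Within one model it leaves the other slopes alone, so it cannot by itself account for anger or support.

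**Step 4. Where do the so-called linear coefficients come from?** The values 0.42, 2.08 and 0.92, and p = 0.606 for support, are the Table 6 rows. Table 4 is the only linear regression table, and PHQ-9, anger, support and stage are not predictors in any of its three models. The opening Results text also gives p < 0.001 for both odds ratios, whereas Table 5 prints 0.002 for anger.

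**Step 5. Is Table 5 consistent with itself?** Assume Wald intervals, so SE = (ln upper - ln lower)/3.92 and p comes from ln(OR)/SE. The interval centre is sqrt(lower × upper).

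| Predictor | Printed OR | Interval centre | p from OR and CI width | Printed p |
|---|---|---|---|---|
| PHQ-9 | 1.32 | 1.36 | 0.0001 | <0.001 |
| Anger | 1.27 | 1.29 | 0.0015 | 0.002 |
| Stress | 1.14 | 1.18 | 0.058 | 0.017 |
| Support | 0.54 | 0.55 | 0.017 | 0.021 |
| Stage | 0.61 | 0.54 | 0.046 | 0.049 |

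The stress p-value does not fit its interval width (0.043 to 0.075 allowing for rounding). The stage interval is clearly off centre: its log-scale arms are 0.614 below and 0.355 above. PHQ-9 and stress are off centre too, and anger slightly so. A Wald interval matching OR 0.61 and p = 0.049 would be about 0.37 to 1.00.

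**The case against.** The best case for the report is that most of the conflict has an innocent explanation.

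- **Stage.** The Discussion mentions an adjustment for stage coding, and step 3 shows that a reversed code would bring the two estimates to the same side of 1. This stands as a possible explanation. It also means that the Table 5 stage result was wrong as read and that Table 6 replaces it.
- **Different models.** Table 6 omits stress, which correlates 0.66 with PHQ-9 in Table 2, so some movement in the other coefficients is expected. This stands, and could account for part of the shift in support. The omission itself is unexplained.
- **Anger.** Its scale is nowhere defined, so a change of unit may lie behind the jump. This stands, and neither table can be blamed. The report still needs to say what one unit is.
- **Support.** The estimate keeps its sign, the Table 6 interval contains 0.54, and the non-significant result is disclosed in three places. The Discussion sentence can be read as contrasting two models. That is fair, but the report never says whether Table 5 is adjusted, so the contrast has no stated meaning. The call for psychosocial care is also supported elsewhere on other grounds.
- **Table 5 arithmetic.** The centring checks assume Wald intervals, and other interval methods need not be centred. This stands. They are a reason to check the output and carry little of the argument. Nor is overlap of intervals a formal test between two fits that appear to use the same patients.
- **Keeping both tables.** If Table 5 were an unadjusted analysis, showing both could be legitimate. But the report labels Table 6 as the correction of Table 5, which makes Table 5 superseded.

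None of this rescues the statement that Table 6 confirms Table 5, or the linear label.

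**Conclusion.** The concern holds and must be fixed before the results are used. Of the five associations in Table 5, only PHQ-9 and anger keep direction and significance in Table 6, and anger's odds ratio changes from 1.27 to 8.00. Stage moves from an apparently lower risk (0.61) to a higher one (2.51), support is no longer distinguishable from no association (0.84, 0.43 to 1.63), and stress has been removed without a reason. The Table 6 logistic coefficients are misreported as linear regression in the Results and again in the Discussion.

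These statements rest on the printed tables and on exponentiating Table 6; they need no assumption about interval method. If a reversed stage code is assumed for Table 5, the stage conflict shrinks to a 1.5-fold difference in the same direction. What then remains unexplained is the size of the anger effect, the loss of significance for support, and the missing stress term.

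**What to change.** 1. Report a single logistic model for severe anxiety on the corrected coding, as odds ratios with 95% confidence intervals, and take every odds ratio and p-value in the text from that fit.
2. Define the coding and units of stage, anger and support, and describe the stage recoding. Include stress or give the reason for leaving it out.
3. Withdraw Table 5 and the odds ratios quoted from it (1.32, 1.27, 0.54). Remove the statements that stage and support are protective and that the corrected model confirms Table 5.
4. In the Results and Discussion, relabel 0.42, 2.08 and 0.92 as logistic log-odds coefficients, and change the Discussion wording that reads 0.92 as an effect on anxiety scores.
5. If Table 6 is kept as final, report support as no detectable association (OR 0.84, 0.43 to 1.63). If the model is refitted, use the new value. Do not rest a recommendation on the direction of a non-significant estimate.

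The cost is at most one refit on existing data and text edits. The suggested protective effect of support is lost.

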**Figure 3. Conceptual Path Model illustrating stress–anxiety relationships.**

The conceptual path model illustrates the indirect relationship between stress and anxiety, mediated by sleep disturbance and impaired daily functioning, with  $\beta$  coefficients indicating the strength of associations.

#### 4- Discussion

The present study provides a comprehensive psychosocial profile of breast cancer patients in Al-Anbar, Iraq, highlighting significant associations between psychological distress, sleep disturbance, disease stage, economic burden, and emotional regulation. The results of our study reveal that depression and anxiety levels were remarkably high among breast cancer patients, with strong correlations to sleep-related variables and the use of sedative medications. These findings are consistent with previous studies from Iraq and neighboring countries, which emphasize the underrecognized psychological morbidity among cancer patients (13).

Specifically, the elevated stress levels observed in our study appear closely tied to poor sleep quality and increased reliance on sedatives. This pattern is consistent with findings from Iranian oncology research, where 66.8% of cancer patients reported poor sleep quality (PSQI > 5), strongly associated with symptoms of anxiety and depression (14)

Similarly, (14) Demonstrated that more than one-third of cancer patients experienced subjective sleep disturbances, with 6.1% relying on sedative medication. These findings highlight disrupted sleep as a key contributor to psychological distress in oncological care and support the growing understanding that impaired sleep quality may serve as a potential clinical indicator of emotional dysregulation in cancer care.

However, other studies have reported conflicting results. For example, (15) found that while sleep disturbances were prevalent among cancer patients, they were not consistently associated with heightened anxiety or depression. Such discrepancies may be explained by differences in patient populations, cancer types, cultural factors, and methodological variations across studies.

The results of the current study revealed that advanced cancer stage was significantly associated with increased levels of psychological distress, particularly anxiety and depression. After adjusting for stage coding, regression models confirmed that advanced cancer stage predicted elevated anxiety scores ( $\beta = 0.92$ ,  $p = 0.001$ ), which aligns with previous findings from oncology populations in the region(16). This association may reflect the psychological impact of disease severity, poor prognosis, increased treatment burden, and concerns about disease progression and its potential complications.

Furthermore, Kruskal-Wallis analysis confirmed significant differences in mean ranks of depression, anxiety, and stress across cancer stages ( $H = 14.76$  to  $31.09$ ,  $p < 0.01$ ). These findings are supported by evidence from Iran and neighboring countries, where patients with stage III and IV breast cancer reported higher rates of emotional distress compared to the early stages of the disease (14). The increased psychological vulnerability in advanced stages underscores the need for stage-specific psychosocial interventions in cancer care protocols

Interestingly, total treatment cost showed a weak but statistically significant inverse correlation with psychological distress variables (e.g., PHQ-9\_Total:  $r = -0.11$ ,  $p = 0.017$ ). Although initially counterintuitive, this finding may reflect a perceived sense of security or access to higher-quality care among patients with greater financial capacity. Similar interpretations were reported in recent findings from Turkey, where patients with access to private sector services and higher financial resources exhibited lower levels of psychological distress despite elevated treatment costs, suggesting that financial ability may buffer emotional burden through enhanced control and perceived care quality (17).

As for psychological support, logistic regression models from this study suggested a protective effect ( $OR = 0.54$ ), though this was not statistically significant in the adjusted model ( $p = 0.606$ ). The lack of significance may be attributed to limited availability or underutilization of structured psychological services in the region, a challenge frequently reported in Iraq and across low-resource Middle Eastern settings. (18,19). Nonetheless, the direction of effect emphasizes the urgent need to integrate psychosocial support into routine oncology care.

Among all predictors examined, depression (PHQ9\_Total) and anger emerged as the strongest independent predictors of severe anxiety in both logistic and linear regression models ( $\beta = 0.42$  and  $2.08$ , respectively,  $p < 0.001$ ). These findings support prior research indicating that depressive symptomatology often precedes or co-occurs with anxiety in cancer patients, especially when emotional regulation is compromised (11)

Although anger remains an underexplored emotional construct in oncology, its relevance is gaining traction. In Iraq, sociocultural norms that discourage emotional expression, combined with the psychological toll of cancer, may intensify internalized anger, contributing to emotional dysregulation. This perspective is supported by findings from the national report, which highlighted elevated psychological distress among cancer patients and emphasized the role of suppressed emotions in shaping anxiety and avoidance behaviors (20).

These findings emphasize the significance of addressing emotional dysregulation, particularly in patients presenting with overlapping symptoms of depression and anxiety.

This suggests that psychological screening tools should incorporate anger-related items to facilitate the early identification of high-risk cases.

The conceptual path model derived from the dataset suggests that stress influences anxiety primarily through indirect mechanisms, notably sleep disturbance and impaired daily functioning. While the direct association between stress and anxiety was minimal ( $r = -0.01$ ), robust indirect effects were observed via sleep problems ( $r = 0.74$ ) and functional impairment ( $r = 0.77$ ). These findings are consistent with regional studies from Egypt and Oman, highlighting sleep disturbance and fatigue as key mediators of psychological distress in oncology patients. (Al-Habsi et al., 2021; Gabra & Hashem, 2021; Hendy et al., 2025).

This structure reinforces theoretical frameworks such as the Transactional Model of Stress and Coping, where maladaptive emotional responses (e.g., stress) translate into clinical outcomes (e.g., anxiety) through sleep and functional capacity mediators. Similar models have been proposed in Jordanian studies (24). Though the present model uniquely incorporates performance and anger as variables of interest, adding depth to the psychosocial profile.

The inclusion of psychological support and its weak inverse association with anxiety ( $r = -0.07$ ) further suggests that strengthening emotional resources could buffer the transition from stress to anxiety. This model may therefore serve as a foundational structure for targeted interventions in Iraqi cancer care systems, particularly in resource-limited settings.

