In Iraq, mental health services incorporation into oncology care remains substantially inadequate. Mental health professionals are scarce in most oncology centers, and psychological screening is not routinely performed during cancer diagnosis or follow-up. Cultural stigma surrounding mental illness may also contribute to the underreporting of emotional symptoms and poor help-seeking behavior. According to a 2023 WHO-EMRO report, less than 15% of patients in Iraq received psychological support, even though studies consistently demonstrate a high rate of undiagnosed mood disorders in this group of patients (12).

The present study aims to examine the psychosocial, clinical, and economic correlations of depression, anxiety, and stress among breast cancer patients in Al-Anbar city. Applying a multidimensional analytic approach, including multivariate linear and logistic regression, ROC analysis, and path modeling. This study explains how individual, emotional, and treatment-related factors interact to shape mental health outcomes. The findings are intended to guide more culturally sensitive and systemically integrated psychological interventions for cancer patients in Iraq and the region.

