### **2-4 Questionnaire tool and data extraction**

Patients' data were collected from medical records (demographics data, medication use history, and clinical profile). Cost data was obtained from the finance department at the center. Financial data included all available direct medical costs, such as treatment and physician visits. Moreover, patients were contacted to estimate the indirect cost associated with breast cancer therapy. A validated assessment tool, the Generalized Anxiety Disorder 7-item (GAD-7) and the Patient Health Questionnaire (PHQ-9) were used to assess anxiety and depression [Spitzer et al., 2006; Kroenke et al., 2001]. The patients were asked to determine the degree of applicability of each item (question) on a 4-point Likert scale. The participants' responses varied from 0 to 3, with 0 denoting "Not at all" and 3 denoting "Nearly every day." Nine elements comprise the PHQ-9 instrument. Items are scored on a scale of 0 to 3, resulting in a total score that ranges from 0 to 27. A total score of 0–4 indicates minimal depression, 5–9 mild depression, 10–14 moderate depression, 15–19 moderately severe depression, and 20–27 severe depression. Seven elements comprise the

GAD-7 instrument. Items are scored on a scale of 0 to 3, resulting in a total score that ranges from 0 to 21. Mild anxiety is indicated by a total score of 5–9, moderate anxiety by 10–14, and severe anxiety by 15–21.

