## **2-6 Data Analysis**

Data was analyzed using IBM SPSS Statistics version 26. Descriptive statistics (mean, standard deviation, frequency, and percentage) were used to summarize demographic and clinical variables. The Kolmogorov-Smirnov test was applied to assess the normality of continuous variables, and due to non-normal distribution, non-parametric tests were used.

Bivariate analyses included Spearman's correlation coefficient to evaluate associations between psychological outcomes (depression, anxiety, stress) and continuous predictors such as sleep quality, cost, and number of children. The Kruskal-Wallis H test was employed to examine differences in distress levels across cancer stages.

Categorical associations were evaluated using Pearson's Chi-square test. Binary logistic regression analysis was conducted to identify predictors of severe anxiety. Additionally, multivariate linear regression models were constructed for each psychological outcome (PHQ-9, GAD-7, stress), and multicollinearity was assessed using the Variance Inflation Factor(VIF).

Receiver Operating Characteristic (ROC) curve analysis was used to assess the predictive accuracy of stress scores for severe anxiety, with Area Under the Curve (AUC) interpreted based on conventional thresholds. Conceptual path modeling was used to explore potential indirect relationships between stress and anxiety, mediated by sleep disturbance and impaired daily performance.

All tests were two-tailed, and a p-value of less than 0.05 was considered statistically significant.

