## 6-Conclusion

This study highlights the multifactorial nature of psychological distress among breast cancer patients in Al-Anbar, Iraq. Depression, anxiety, and stress were significantly linked to sleep disruption, sedative use, disease stage, and emotional dysregulation. Advanced cancer stage emerged as a key predictor of heightened anxiety and depression. These findings emphasize the need to integrate psychosocial assessment and targeted interventions into oncological care, particularly in low-resource settings, to mitigate psychological morbidity and improve quality of life in this population.

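### The Discussion explains only the weak inverse cost–distress correlation, omits Table 4's positive adjusted cost coefficient for PHQ-9, and offers a financial-capacity mechanism that no documented variable measures

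*Combined protocol and SAP*

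**What the plan says.** Economic correlates belong to the stated aim in the Introduction: "The present study aims to examine the psychosocial, clinical, and economic correlations of depression, anxiety, and stress among breast cancer patients". Section 2-6 (Data Analysis) assigns Spearman correlation to continuous predictors, cost among them. It then adds a multivariable linear model for each outcome and sets the threshold: "All tests were two-tailed, and a p-value of less than 0.05 was considered statistically significant". It gives no multiplicity rule.

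The Discussion opens by "highlighting significant associations between psychological distress, sleep disturbance, disease stage, economic burden, and emotional regulation". Its cost paragraph states: "Interestingly, total treatment cost showed a weak but statistically significant inverse correlation with psychological distress variables", giving r = -0.11 and p = 0.017 for PHQ-9. It then suggests that "this finding may reflect a perceived sense of security or access to higher-quality care among patients with greater financial capacity" and cites a Turkish study for a similar reading.

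Table 4 prints adjusted Total Cost coefficients of +7.5E-5 for PHQ-9 (t = 2.209, p = 0.028), +3.0E-5 for GAD-7 (t = 1.246, p = 0.213) and +3.4E-6 for stress (t = 0.711, p = 0.477). The sentence under Table 4 names only sedative use and sleep-related worry.

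Section 2-4 lists the record data as "medical records (demographics data, medication use history, and clinical profile"), together with direct costs from the centre and indirect costs estimated by contacting patients.

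**The concern.** On one of its stated aims, the study gives the reader a single direction and a reason for it. It does not say that its own depression model has the opposite sign. All three rank correlations are negative and all three adjusted slopes are positive, but only the first set is discussed.

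The next paragraph of the Discussion handles psychological support differently. There the reader is told of an apparent protective effect, "though this was not statistically significant in the adjusted model". No such notice is given for cost, where the sign itself changes.

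The mechanism has no support in the data described. Cost incurred is not ability to pay, and no variable for income, insurance, payer, perceived security or perceived quality of care appears in section 2-4 or in Tables 1 to 6. The record demographics are not itemised, so an undocumented income item cannot be ruled out, but none is described or analysed. The title of the cited Turkish study, as printed in the References, links greater financial toxicity to more distress. A title does not settle what that study found, and financial toxicity is not cost, but it is a further reason to treat the explanation as untested.

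**Working it through.** **Inputs.** n = 500. Table 1: cost mean 3721.69, SD 4456.79, range 80 to 34785; SDs of PHQ-9 6.11, GAD-7 3.81. Table 2: the three cost correlations. Table 4: B, t, p, the cost VIF of 1.022, and R² of 0.702 (PHQ-9) and 0.615 (GAD-7).

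**1. The stated correlation reproduces.** With t = r√[(n-2)/(1-r²)] on 498 df, r = -0.11 gives t = -2.470 and p = 0.0139. The printed p = 0.017 corresponds to r = -0.107, which rounds to -0.11.

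**2. The Table 4 cost rows reproduce.** For PHQ-9, t = 2.209 on 493 df (500 - 6 - 1) gives p = 0.0276, printed as 0.028. GAD-7 and stress give 0.213 and 0.477, as printed. For PHQ-9 the standard error from B/t is 7.5E-5/2.209 = 3.40E-5. Rebuilt from other printed figures it is (6.11/4456.79)·√[(1-0.702)·1.022/493] = 3.41E-5. The size of the coefficient is therefore internally consistent. This does not check its sign.

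**3. Both analyses side by side.** Correlation CIs use Fisher's z with SE √[(1+r²/2)/(n-3)]. Slopes are B × 4456.79, with SE = slope/t.

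| Outcome | Spearman r (95% CI) | Adjusted slope per SD of cost (95% CI) |
|---|---|---|
| PHQ-9 | -0.11 (-0.20 to -0.02) | +0.33 (0.04 to 0.63) |
| GAD-7 | -0.10 (-0.19 to -0.01) | +0.13 (-0.08 to 0.34) |
| Stress | -0.12 (-0.21 to -0.03) | +0.015 (-0.03 to 0.06) |

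Squaring the correlations gives 1.0% to 1.4% of rank variance. The standardised PHQ-9 slope is 7.5E-5 × 4456.79/6.11 = 0.055.

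**4. Could adjustment alone explain the PHQ-9 reversal?** A VIF of 1.022 means that the multiple correlation of cost with the other predictors is √(1 - 1/1.022) = 0.147. With R² = 0.702 and standardised slope 0.0547, the linear part due to the other predictors has SD of at most 0.844 in the extreme case, where it is aligned as negatively as possible with cost. The raw Pearson correlation can then be no lower than 0.0547 - 0.147 × 0.844 = -0.069. Adjustment can reverse the sign, but it moves the estimate by at most 0.124. The gap from -0.107 to +0.055 is 0.162, which leaves about 0.04. For GAD-7 the limit is 0.116 of a gap of 0.135, which leaves about 0.02. The remainder points to rank versus raw scale (cost is strongly right-skewed, with an SD above its mean) or to coding.

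**5. Illustration only: three outcomes, Bonferroni.** PHQ-9: 3 × 0.017 = 0.051 (rank; 0.042 if r is exactly -0.11) and 3 × 0.0276 = 0.083 (adjusted). GAD-7 rank: 3 × 0.0253 = 0.076. Stress rank: 3 × 0.0072 = 0.022, although the adjusted stress slope cannot be distinguished from zero.

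**6. Labels in Table 4.** Sleep Satisfaction has VIF 1.021 in the PHQ-9 model and 4.866 in the GAD-7 model; 4.866 is also the VIF of Sleep Difficulty in the PHQ-9 model. For Sleep Difficulty to have VIF 4.866, the contributions of the other five predictors must sum to 3.866. Their printed VIFs allow at most √4.866 × (√0.766 + √0.021 + √0.039 + √0.022 + √0.048) = 3.50. The printed labels and VIFs cannot all belong to one six-predictor model.

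**The case against.** The strongest reply is that the Discussion reports the test that section 2-6 assigns to cost, calls the correlation weak, and words the explanation as a possibility backed by an outside source. Nothing is hidden, since all three coefficients are printed. A rank correlation and a raw-scale adjusted slope may validly differ. Because the labels in Table 4 are inconsistent, the covariate set behind the adjusted coefficient is uncertain. The effects are tiny and the conclusions do not use cost.

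Much of this stands. There is no arithmetic error, and using Spearman for cost is what the methods say. The comparison with psychological support is imperfect, because that contrast is between two logistic models of one outcome. The opening mention of economic burden states no direction and is true in the nominal sense, so changing it is optional. The calculation in step 4 mixes a rank correlation with a linear slope and is only a limit. The label problem should be settled first.

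The omission remains. The multivariable models are also named in the aim and the methods. Tentative wording about a mechanism does not disclose a contrary result, and a coefficient of 7.5E-5 in a table row does not tell the reader that the direction depends on the model. A cited study is not a measurement in this sample.

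**Conclusion.** The concern holds. The Discussion presents an inverse association with a mechanism, while the study's printed results support only a weak, model-dependent association. For PHQ-9 the rank correlation is -0.11 and the adjusted slope is +0.33 points per SD of cost. Both are nominally significant and neither direction is established. For GAD-7 and stress the adjusted slopes are positive but compatible with zero. The financial-capacity explanation is untested.

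This rests on the Table 4 cost rows being correctly coded and signed. The limit in step 4 also assumes that the printed VIF and R² come from the same model. The Bonferroni figures play no part in the conclusion.

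The reach is one Discussion paragraph and, optionally, one item in its opening list. The Conclusion names other factors only: "Depression, anxiety, and stress were significantly linked to sleep disruption, sedative use, disease stage, and emotional dysregulation". The change should be made, but it does not alter the study's main messages.

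**What to change.** 1. Check the coding and sign of cost in Table 4, and resolve the predictor labels and VIFs, before anything is rewritten.
2. Show the three adjusted cost coefficients with confidence intervals beside the Table 2 correlations. State in the Discussion that the adjusted PHQ-9 coefficient is positive and that the cause of the difference is not established.
3. Add a sensitivity analysis with cost on a log or rank scale, unadjusted and adjusted, with and without the sleep and sedative variables. Those variables may be near-proxies of distress: the Results report r > 0.90 for sedative use.
4. Remove the financial-capacity explanation, or state plainly that this study did not test it.
5. Describe the cost–distress association as weak and model-dependent, and preferably qualify the opening mention of economic burden to match. Agreement in sign between unadjusted and adjusted estimates should not be used as a decision rule, because they may validly differ.

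The cost is a coding and label check, a few model runs on existing data, one extra table and one rewritten paragraph. The price is a weaker interpretive statement about cost.
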